Formative evaluation (Aim 3). Through mixed quantitative and qualitative methods, we will explore patient- and *practitioner-centered* treatment acceptability and process of the two methods of OSA management. Quantitative: We will evaluate participant acceptance of web-based OSA management versus in-person management by comparing the between-group differences in process indicators, including attrition and therapeutic alliance. *We will evaluate practitioner acceptance of web-based OSA management versus in-person management by comparing the between-group differences in therapeutic alliance.* WAI-SR and CSQ-8 are patient-oriented scales which have been used widely as process indicators in research comparing delivery of treatment via telemedicine versus in-person format. Qualitative: We will conduct semi-structured phone interviews with a subset of up to 45 participants: 15 who complete the first 3-mo web-based intervention, 15 patients who complete the 3-mo in-person management, and 15 patients who drop out of either intervention group. Each patient will be interviewed over the phone by [name] who has extensive expertise in qualitative interviewing. The phone interviews will be conducted within one month of the participant completing either the first 3 months of PAP intervention or dropping out of the study. Phone interviews rather than in-person interviews were chosen for a number of reasons: the relatively non-sensitive nature of the interview topic; to decrease burden on patients; and to increase likelihood of successfully completing the targeted number of interviews. A semi-structured interview guide will be developed by [name] and revised in consultation with the research team. The interview guide will cover topics including: the participant's experiences with OSA; expectations going into treatment; attitudes, opinions, and experiences with treatment; reasons for dropping out (if relevant); perceived barriers and facilitators to continuing treatment; perceived therapeutic relationship with the provider; and suggestions for making treatment more patient-centered. We anticipate we will reach 'theme saturation' (where no new concepts emerge in the data) after completing approximately 12 interviews with patients from each group. Each interview will be audio-recorded and last between 30-60 minutes.

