**Analysis of secondary clinical outcomes in Aim 1.** Secondary outcomes in Aim 1 include changes from baseline to Month 3 in scores of the ESS, SF-12 (physical and mental health components), and CES-D questionnaires. For each secondary outcome, analogous analyses of covariance models will be used to determine least squares adjusted treatment group differences in mean change along with 95% confidence

intervals since non-inferiority deltas are not pre-specified. Baseline values of the outcome measures will be included in their respective ANCOVA models. The above results will be interpreted as hypothesis generating.

**Missing data methods.** The mixed model approach uses information in the covariance matrix of predictors and outcomes over time to implicitly impute missing 3-month FOSQ values. Of note, participants will complete the assessment battery at 1-month following initiation of treatment. Therefore, subjects missing month 3 results will not be excluded. These imputations are valid if the likelihood of missingness is independent of treatment group, conditional on observed data included in the model, i.e., if missing data are missing at random (MAR). For comparison with earlier studies, we will also perform the analyses using the last observation carried forward method. Finally, in sensitivity analyses, we will evaluate the impact of departure from the assumed MAR mechanism by using multiple imputation (MI) to implement a selection model approach. In this way, we will be able to compare estimated effects based on different assumptions about the missingness mechanism, and to assess the sensitivity of our estimates to these assumptions. If data on predictors is incomplete, we will use multiple imputation methods (as implemented in SAS PROC MI and MIANALYZE) to generate multiple imputed complete datasets, perform analyses, and then combine analysis results to produce estimates that are asymptotically unbiased, with standard errors that account for imputation uncertainty.

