**Modified intent-to-treat and per-protocol populations.** Primary analysis for non-inferiority will be based on all randomized participants initiated on APAP with at least one FOSQ follow-up score. In a secondary analysis, the non-inferiority test will be repeated using a per protocol cohort (patients who have been initiated on APAP and have non-missing endpoints at month 3), since protocol violations can add noise making it more difficult to distinguish between the two active treatment groups.

**Statistical methods for Aim 2.** Aim 2 will determine if REVAMP management of patients with OSA is cost-effective compared with in-person care. The perspective of the analysis will be that of the VA. While the VA has the general well-being of veterans as its goal, we will focus our attention on health care costs, in part because VHA patients with OSA are older and less likely to work. The analyses for Aim 2 will be based on all randomized participants, as this is the target population for the evaluation of Aim 2 and Aim 3 outcomes related to management of this patient population. We will perform a secondary analysis using the modified intention to treat sample (Aim 1 analysis set). The primary outcome measure in Aim 2 will be the difference in sleep-related cost between the two delivery modalities. Our hypothesis is 2a)  $H_0: \Delta C = 0$  vs  $H_A: \Delta C < 0$ . Based on data from our prior study of home vs in-lab diagnosis, we assume average 3-month sleep-related costs of \$1755 (SD, 745) for the home group and of \$2538 (SD, 1065) for the in-lab group. Resulting power is 1.0 for sample size of 114 per group and remains greater than 0.9 if, when including participants without OSA on HST and participants with CSA/CSR, the means are reduced by 25% and the SDs are increased by 25%.

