**Statistical methods for Aim 3, Quantitative component.** Aim 3 will compare patient-centered treatment acceptability and process measures of the two management approaches. We will evaluate patient acceptance of telemedicine-based care by comparing the between-group differences in attrition, therapeutic alliance, and satisfaction with care. The primary quantitative objective outcome measure in Aim 3 will be percent of patients who drop out of each treatment. The primary subjective outcome measures will be change in the WAI-SR and CSQ-8 scores. For this exploratory aim we will estimate mean values and confidence intervals. Mixed effects models will be used to estimate the between-groups difference in means and confidence intervals, for each of

the outcome measures. Results will be ascertained via ITT and per-protocol procedures as previously discussed. A series of mixed models is proposed for each outcome identified in Aim 3 (WAI-SR, CSQ-8).

Qualitative data analysis. Interviews will be digitally recorded with the participant's permission, transcribed by a professional transcriptionist, and prepared as primary documents to be loaded into Atlas.ti software for data management and analysis. Atlas.ti is a software program designed to assist in the management and analysis of qualitative data, including primary documents (e.g., transcripts), secondary notes (e.g., memos written by the investigators concerning methodological issues), and analytical notes (e.g., emerging theories to be tested through further data collection and analysis). Atlas is particularly suited to the constant comparative method most closely associated with grounded theory, adapted for use in healthcare and health services research. Analysis of patient interviews will be guided by Aim 3: to identify patient perspectives, attitudes, and preferences regarding REVAMP versus in-person management of patients with OSA, as well as barriers and facilitators to participation in either clinical pathway. *Similarly, analysis of provider interviews will focus on identifying providers' attitudes and perspectives on acceptability of delivering care via REVAMP vs. in-person, and perceived barriers and facilitators to implementation, spread, and maintenance of REVAMP as a means to deliver treatment for patients with OSA.*

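### The per-protocol set is justified by protocol violations but has no violation criterion, so the secondary non-inferiority test is a completer analysis

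*Combined protocol and SAP*

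**What the plan says.** Under *Modified intent-to-treat and per-protocol populations*, the primary non-inferiority set is "all randomized participants initiated on APAP with at least one FOSQ follow-up score". A secondary analysis repeats the test in a per-protocol cohort, defined as "patients who have been initiated on APAP and have non-missing endpoints at month 3". The reason given is "since protocol violations can add noise making it more difficult to distinguish between the two active treatment groups".

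*Missing data methods* states that "subjects missing month 3 results will not be excluded" from the primary analysis, because a 1-month score is also collected.

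For Aim 3, *Statistical methods for Aim 3, Quantitative component* makes "percent of patients who drop out of each treatment" the primary objective outcome. After describing the mixed models it adds: "Results will be ascertained via ITT and per-protocol procedures as previously discussed". The paragraph on Aim 2 names all randomized participants as the population for both later aims.

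**The concern.** A per-protocol analysis in a non-inferiority trial is there to show whether departures from the protocol have pulled the arms together, since that favours the hypothesis the trial hopes to support. The plan gives this very reason. Its definition, however, selects on data completeness. A participant enrolled against the eligibility criteria, or managed in the other arm's mode without any provision for it, stays in the cohort if the month-3 data exist.

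At stake is how the secondary result is read. If the two analyses agree, a reader will take it that violations did not matter, when the comparison speaks only to people without month-3 data. That question is already covered in *Missing data methods* by the mixed model, last observation carried forward and a selection-model sensitivity analysis. The question about violations is left unanswered.

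The same cohort also appears to be carried into Aim 3, where one outcome is drop-out itself.

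**Working it through.** **Definition against purpose**

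| | Primary set | Per-protocol set |
|---|---|---|
| APAP initiated | required | required |
| FOSQ-10 follow-up | at least one score | month-3 score |
| Eligibility confirmed | no criterion | no criterion |
| Care in the assigned mode | no criterion | no criterion |
| Other violation | no criterion | no criterion |

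For FOSQ-10 the only row that differs is follow-up data. The phrase on non-missing endpoints also does not say whether FOSQ-10, APAP use or both are needed.

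**The plan's own figures** (*Sample size, and power* and the enrolment paragraph after it: margin 1, SD 2.80, one-sided α 0.05, power 85%, 20% without OSA, 20% drop-out after APAP start)

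- n per group = 2 × (1.645 + 1.036)² × 2.80² / 1² = 112.7, so 113; the plan has 114.
- Power at 114: SE = 2.80 × √(2/114) = 0.371; Φ(1/0.371 − 1.645) = 85.3%. Reproduced.
- Enrolment: 228 / (0.8 × 0.8) = 356.25; the plan has 356. Reproduced.

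**How far the two sets can differ**

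- APAP starters: 356 × 0.8 = 284.8.
- Drop-outs among them: 284.8 × 0.2 = 57.0.
- Completers: 284.8 − 57.0 = 227.8, or 114 per group.

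If drop-out means no month-3 score, the per-protocol set is these 228 completers. The primary set has 228 to 285 members, depending on how many drop-outs gave a 1-month score. At least 228/285 = 80% of the primary set is therefore in both, including any violator with month-3 data.

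**Aim 3 drop-out**

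The planned rate among APAP starters is 20%. If drop-out means loss before month 3, the rate in a set that requires month-3 data is 0% in both arms by construction.

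**Cost of a real violation criterion** (exclusion of 10% of each arm is assumed)

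114 × 0.9 = 102.6, taken as 102 per group.

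- FOSQ-10: SE = 2.80 × √(2/102) = 0.392; power = Φ(1/0.392 − 1.645) = 81.7%.
- APAP use (margin 0.75, SD 2.2): SE = 2.2 × √(2/102) = 0.308; power = Φ(0.75/0.308 − 1.645) = 78.5%, against 82.4% at 114.

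For FOSQ-10, exclusion of 5% or 20% would give 83.6% or 77.8%.

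**Illustration of wrong-mode care** (all rates assumed)

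Suppose the true difference is −1 among those managed as assigned, and a share v of REVAMP participants is in effect managed in person, with no difference from the other arm. The arm difference is then −(1 − v), and the chance of declaring non-inferiority is 1 − Φ(1.645 − v/0.371):

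| v | 0 | 5% | 10% | 20% | 30% |
|---|---|---|---|---|---|
| Chance | 5.0% | 6.6% | 8.5% | 13.4% | 20.2% |

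The cohort as written leaves these figures unchanged if those participants have month-3 data.

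**The case against.** Several objections carry weight.

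- **Permitted care is not contamination.** *REVAMP pathway* allows an in-person appointment when a problem cannot be resolved by telephone, and the in-person arm may receive extra calls. This stands. A rule that demanded every follow-up in the assigned mode would remove the harder REVAMP cases after randomization, with no matching step in the other arm, and could itself favour non-inferiority.
- **The illustrated error rates are not the trial's error rate.** A reader might infer that false non-inferiority rises to 8.5% or 13.4%. The documents do not support that: they neither report nor expect unplanned switching. The stated hypotheses compare arm means, and an arm difference of −0.9 or −0.8 lies within the margin. The inflation refers only to the effect among those managed as assigned.
- **The cohort does lose some violators.** It would be too strong to say that it removes none. Those who also lack month-3 data drop out of it, and a missed month-3 questionnaire is itself a departure from the schedule. But nobody is removed because of a violation.
- **Per-protocol drop-out need not be zero.** The Aim 3 outcome is dropping out of treatment, while *Formative evaluation (Aim 3)* speaks of "completing either the first 3 months of PAP intervention or dropping out of the study". Someone who stops PAP can still answer the month-3 web questionnaire, and so be both in the set and a drop-out. The sentence on ITT and per-protocol procedures may also be meant only for WAI-SR and CSQ-8. Zero follows only under one reading, which the plan neither adopts nor excludes.
- **The analysis is secondary.** No section makes the non-inferiority conclusion depend on it, and Aim 3 is exploratory. This limits the consequence but does not repair the definition.

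**Conclusion.** The point holds as a mismatch between a stated purpose and a stated rule. The per-protocol cohort excludes only APAP starters without month-3 endpoints. Violators with month-3 data remain, so the secondary non-inferiority test is a completer analysis and does not check the effect of violations. This follows from the text and needs no assumption about how many violations will occur.

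The size is moderate. At the plan's rates the two sets can differ by at most about 57 of 285 people, none of them chosen for a violation. How much violations would change the result cannot be worked out from the documents.

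For Aim 3 the conclusion is conditional: drop-out in this cohort is 0% by construction if drop-out means loss before month 3, and the plan never defines the term.

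**What to change.** Amend the analysis plan before the month-3 data are examined.

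1. Define the per-protocol set as modified intent-to-treat participants who met the eligibility criteria, had no major protocol violation, and have month-3 data for the endpoint analysed.
2. List the major violations. Include care given in the other arm's mode outside what the protocol permits. State that in-person escalation allowed under *REVAMP pathway* is not a violation and does not lead to exclusion. The type of each encounter is already documented in both arms.
3. Do not use APAP hours as a criterion, because they are the Hypothesis 1b endpoint.
4. For Aim 3, define drop-out and report it on all randomized participants only, which matches the population already named for that aim.

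If the sponsor prefers not to define violations, the alternative to items 1 to 3 is to rename the existing set *completers* and remove the protocol-violation rationale.

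The cost is wording, plus a somewhat smaller per-protocol sample. If 10% of each arm were excluded, power would be about 82% for FOSQ-10 and 79% for APAP use. The primary analysis and the enrolment target do not change.

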Other than the above requirements, each site will conduct in-person management according to their usual clinical practice. The decision to allow each site to conduct its current in-person clinical care will make our findings more generalizable. Not having to replicate the exact same conditions for in-person management at the sites reduces the cost of the project. We realize that allowing these differences at the 3 sites raises the possibility of a site-related bias. We will assess this by including site as a covariate in the analysis models.

*Home sleep testing and polysomnogram.* Participants in both the in-person and REVAMP arms will have an HST as their first diagnostic test, but their practitioners will have the ability to order an in-lab PSG when clinically indicated. A technically acceptable HST will require at least a 3 hr recording of oxygen saturation and one respiratory signal. Recordings that are technically inadequate will be repeated once. If the repeat HST is not of acceptable quality, the participant will be scheduled for an in-lab PSG performed according to AASM recommended guidelines. To reduce the possibility of a false negative HST result, participants with an AHI < 5 events/hr on initial HST will repeat the study. Participants with two negative HSTs will be advised that they may still have OSA and, if clinically indicated, can be offered the option of an in-laboratory PSG.

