Secondary outcome measures include the difference in total costs, the difference in QALYs, and the ratios of the differences in cost and QALYs. The secondary hypothesis for the cost-effectiveness ratio is 2b)  $H_0: \Delta C/\Delta Q > 100,000$  vs  $H_A: \Delta C/\Delta Q \leq 100,000$ . As with the efficacy and non-inferiority analyses, the cost difference ( $\Delta C$ ) and the preference score difference ( $\Delta Q$ ) will be estimated using mixed effect models for longitudinal data. QALYs will be constructed by taking the area under the quality-adjusted survival curve. The cost-effectiveness ratio ( $\Delta C/\Delta Q$ ) will be calculated by dividing the estimated difference in cost by the estimated difference in QALYs. Confidence intervals for the cost-effectiveness ratios will be calculated using Fieller's theorem method. A point estimate less than 100,000/QALY and a 90% confidence interval that excludes \$100,000 will be evidence that we can reject the null hypothesis that the incremental cost-effectiveness ratio is not less than \$100,000.

Costs, QALYs, and cost-effectiveness ratios will be calculated for costs and effects during the first 3 months following initiation of APAP treatment and for the full period of follow-up (maximum, 2 years). The study design (follow-up extending from enrollment until 3 months after last patient is enrolled) introduces substantial administrative censoring that – as with the primary analysis – will be addressed by use of a mixed model approach (i.e., patients will have different lengths of follow-up, and thus different costs and QALYs, simply because they were enrolled at different times). Because this censoring is due primarily to administrative reasons, it is generally considered to yield data that are missing completely at random (MCAR). While use of the electronic medical records for the collection of cost data will lead to limited missing cost data, there may be censoring of cost data for services outside the VHA and of the QALY measures due to loss to follow-up. If such drop-out is related to disease severity or to outcomes after randomization, it generally would be considered to yield data that are either missing at random (MAR) or that are non-ignorably missing.

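### Aim 2 is meant to decide cost-effectiveness, but its only powered test covers sleep-related cost alone, and the secondary ratio rule can be met when REVAMP is cheaper, worse and a net loss

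*Combined protocol and SAP*

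**What the plan says.** All of the following is in the combined protocol and SAP, STATISTICAL ANALYSIS, under Statistical methods for Aim 2, unless another place is named.

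- The purpose: "Aim 2 will determine if REVAMP management of patients with OSA is cost-effective compared with in-person care".
- The primary outcome: "The primary outcome measure in Aim 2 will be the difference in sleep-related cost between the two delivery modalities". Hypothesis 2a tests a cost difference of zero against a saving, in all randomized participants. A secondary analysis uses the Aim 1 set.
- The planning figures: "average 3-month sleep-related costs of \$1755 (SD, 745) for the home group and of \$2538 (SD, 1065) for the in-lab group", introduced with "Based on data from our prior study of home vs in-lab diagnosis".
- The power: "Resulting power is 1.0 for sample size of 114 per group". It is said to stay above 0.9 if the means fall by a quarter and the SDs rise by a quarter.
- The rest: "Secondary outcome measures include the difference in total costs, the difference in QALYs, and the ratios of the differences in cost and QALYs". Hypothesis 2b is met when the estimated ratio is below $100,000 per QALY and the 90% Fieller interval excludes that value. No power is given for 2b.
- On diagnosis, under Home sleep testing and polysomnogram: "Participants in both the in-person and REVAMP arms will have an HST as their first diagnostic test".

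**The concern.** A cost-effectiveness conclusion needs cost and health together. Test 2a uses only cost, and only the sleep-related part of it. The cost of treatment and equipment is counted, so an arm in which fewer participants start or continue PAP can look favourable on 2a. When in-person visits are replaced by remote care, that is the possibility a reader most wants excluded.

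Hypothesis 2b does use health, but its inequality points the wrong way in the case that matters. When REVAMP is cheaper and health is worse, the ratio is dollars saved per QALY given up. A low ratio then means too little was saved for the health lost, yet 2b counts it as success. Both Aim 2 tests could therefore favour REVAMP when, at the plan's own threshold, it is a net loss. The text does not say what a rejected 2a, alone or with 2b, allows the sponsor to conclude.

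**Working it through.** **Inputs from the plan.** Mean 3-month sleep-related cost $1755 (SD 745) against $2538 (SD 1065), so a saving of $783; 114 per group for power; 356 randomized, so about 178 per group in the Aim 2 set; threshold $100,000 per QALY.

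**Assumed.** One-sided alpha 0.05 for 2a (none is stated). QALY SD 0.01 to 0.03 per participant and zero correlation between cost and QALYs (the documents give neither).

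**1. The plan's power for 2a reproduces.**
- Planning case: SE = sqrt((745² + 1065²)/114) = 121.7; 783/121.7 = 6.43; power above 0.999.
- 25% scenario: saving 0.75 × 783 = 587.25; SDs 931.25 and 1331.25; SE = 152.2; power = Φ(587.25/152.2 − 1.645) = 0.987. At 178 per group, SE = 121.8 and power = 0.999.
- No health term enters, so these rates hold at any true QALY difference.

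**2. Health loss that cancels the saving.**
- 783/100,000 = 0.00783 QALY; over 0.25 year, 0.00783/0.25 = 0.031 in utility.
- 25% scenario: 0.00587 QALY, or 0.023 in utility.
- At the first of these points 2a still rejects more than 99.9% of the time, and at the second 98.7%. A one-sided 0.05 net-benefit test passes about 5% of the time at either.

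**3. Dependence on the planned saving (2a, uninflated SDs).**

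| True saving | 114 per group | 178 per group |
|---|---|---|
| $783 | >0.999 | >0.999 |
| $391.50 | 0.94 | 0.99 |
| $195.75 | 0.49 | 0.64 |
| 0 | 0.05 | 0.05 |

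**4. Rule 2b when REVAMP is cheaper and worse.** Take a saving of $783 and a loss of 0.01566 QALY, twice break-even.
- Ratio = −783/−0.01566 = $50,000 per QALY, which is below the threshold.
- Net benefit = 100,000 × (−0.01566) + 783 = −$783.

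Simulated from the joint normal sampling distribution (40,000 draws, 114 per group):

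| Assumed QALY SD | 2b met | Net-benefit rule met |
|---|---|---|
| 0.01 | 99.6% | about 0% |
| 0.02 | 85% | about 0% |
| 0.03 | 59% | about 0% |

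Rule 2b also errs the other way. With a $783 saving and no true QALY difference it is met only about half the time (48% to 50%), because a slightly negative QALY estimate turns the ratio into a large positive number.

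**5. Illustration of under-treatment (assumed inputs).** Suppose a participant not on PAP costs $500, $1000 or $1500 less, care is otherwise equally costly, and 20 points fewer REVAMP participants are on PAP. With the inflated SDs at 178 per group, 2a rejects with probability Φ(0.20 × G/121.8 − 1.645), where G is that cost difference. This gives about 20%, 50% and 79%.

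**The case against.** The plan never says that rejecting 2a establishes cost-effectiveness. It gives that question a separate hypothesis, threshold and rule, and ranking cost first is a legitimate design choice. If REVAMP truly costs less, rejecting 2a is a correct result and not a false positive. All of this stands. A reader might infer that the sponsor intends 2a alone to decide the aim; the documents do not support that.

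A reader might also infer that 2a will reject almost whatever happens. That holds only near the planning costs. They come from a comparison of home with in-laboratory diagnosis, whereas both arms here begin with home testing, so the true saving may be smaller. Nor does any figure in the documents suggest that a utility loss of 0.031 is likely.

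There are partial safeguards. Aim 1 requires non-inferiority on both FOSQ-10 and adherence. The section on controlling patient wait time reads similar clinical outcomes and cost-effectiveness together. The secondary cost analysis uses the Aim 1 set, and Aim 3 compares drop-out by arm. In the text available, however, none is made a condition of the Aim 2 conclusion. The Aim 1 primary analysis covers participants started on APAP with a follow-up FOSQ score, so it cannot show a difference between arms in how many start. The documents give no mapping from FOSQ-10 to utility, so whether the 1-point margin would catch such a loss cannot be computed.

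**Conclusion.** The concern holds in this form: the powered Aim 2 test cannot support the conclusion the aim is written to reach, and the rule that should supply the health side misclassifies the cheaper-and-worse case. The break-even loss of 0.0078 QALY and the $50,000 example follow from the plan's own figures and threshold. The rejection rates for 2a rest on the planning costs and the assumed one-sided 0.05. The 59% to 99.6% for 2b rests on the assumed QALY SDs and zero correlation. The missing health term in 2a and the direction of 2b do not depend on any of these. This should be corrected before analysis. It does not invalidate 2a as a test of cost.

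**What to change.** Under Statistical methods for Aim 2:

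1. Keep 2a as the primary cost test, and state that rejecting it supports only lower sleep-related cost.
2. Replace the 2b ratio rule with incremental net monetary benefit in all randomized participants. Conclude cost-effective only if the one-sided 95% lower bound of (100,000 × dQ − dC) exceeds 0, where dQ and dC are REVAMP minus in-person and QALYs come from the SF-6D.
3. Name in advance whether dC is sleep-related or total cost, and whether the horizon is 3 months or full follow-up.
4. Beside the 2a result, report by arm the percent started on PAP and the percent on PAP at 3 months.

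No new data are needed. The cost is that cost-effectiveness becomes harder to claim than lower cost. With a $783 saving and no health loss, power of the new rule for QALY SD 0.01, 0.02 and 0.03 is about 99.6%, 85% and 59% at 114 per group, and about 100%, 96% and 76% at 178. In the 25% scenario at 114 per group it is about 90%, 61% and 40%. These figures use the sleep-related cost SDs; the documents give none for total cost, so power would need to be worked out again if total cost is chosen. The stated power of 1.0 should be attached to the cost claim only.

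### The Hypothesis 2b rejection rule points the wrong way whenever the estimated QALY difference is negative

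*Combined protocol and SAP*

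**What the plan says.** All of this is in the combined protocol and SAP, Statistical Analysis, under the Statistical methods for Aim 2.

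- Hypothesis 2b is an inequality on the bare ratio: H0 is dC/dQ > 100,000 and HA is dC/dQ ≤ 100,000.
- The ratio is obtained by "dividing the estimated difference in cost by the estimated difference in QALYs".
- "Confidence intervals for the cost-effectiveness ratios will be calculated using" Fieller's theorem.
- H0 is rejected on "A point estimate less than 100,000/QALY and a 90% confidence interval that excludes" $100,000.
- The status is secondary: "Secondary outcome measures include the difference in total costs, the difference in QALYs, and the ratios of the differences in cost and QALYs".
- Two horizons are planned: "during the first 3 months following initiation of APAP treatment and for the full period of follow-up (maximum, 2 years").

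No part of the document makes the rule depend on the sign of dQ, refers to dominance or to quadrants of the cost-effectiveness plane, or uses net benefit.

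**The concern.** A cost-effectiveness ratio has no fixed meaning until the sign of its denominator is known. A ratio of −39,150 can be a saving with a QALY gain or an extra cost with a QALY loss. A ratio of +39,150 can be a gain bought at an acceptable price, or a loss that saves only $39,150 per QALY given up. The rule treats all four as success once the interval excludes 100,000.

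Two errors follow when estimated dQ is negative and the interval excludes 100,000:

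- **(a) Claim withheld.** Net benefit is significantly positive, because the saving outweighs a small QALY loss, but the ratio lies above 100,000 and H0 is not rejected.
- **(b) Claim made against the data.** Net benefit is significantly negative, but the ratio lies below 100,000 and H0 is rejected.

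A negative estimate is an ordinary outcome in this trial. The primary aim is non-inferiority and savings are expected. If true QALYs are equal, estimated dQ is negative about half the time.

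**Working it through.** **Inputs from the document.** Three-month sleep-related cost is $1,755 (SD 745) and $2,538 (SD 1,065), so dC = −783. Group size is 114, or 356/2 = 178 for all randomized participants, which is the Aim 2 analysis set. In the diluted case "the means are reduced by 25% and the SDs are increased by 25"%, giving dC = −587.25 and SDs of 931.25 and 1,331.25.

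**Assumed, not in the document.** The SD of 3-month QALYs is taken as 0.02 / 0.03 / 0.05 (SD 0.08 / 0.12 / 0.20 in mean utility over 0.25 year). Cost and QALYs are uncorrelated unless stated. A total-cost SD of 5,000 is used where noted.

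**Step 1: the plan's own figure.** No power is stated for 2b. For 2a the plan says "Resulting power is 1.0 for sample size of 114 per group". Pooled SD = √((745² + 1,065²)/2) = 919.0; SE = 919.0 × √(2/114) = 121.7; 783/121.7 = 6.43; power 1.000. Diluted: 587.25/(1,148.8 × √(2/114)) = 3.86; power 0.987 one-sided or 0.971 two-sided at an assumed α of 0.05. Both agree with the plan, so the cost inputs are read correctly.

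**Step 2: algebra.** Let L = 100,000 and NB = L·dQ − dC. The 90% Fieller set excludes L exactly when (dC − L·dQ)² > 1.645² × Var(dC − L·dQ), that is, when |NB|/SE(NB) > 1.645. Since L − dC/dQ = NB/dQ, the condition that the ratio is below L means NB > 0 if dQ > 0 and NB < 0 if dQ < 0. No assumed input is needed.

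**Step 3: mirror example.** Diluted SDs, 178 per arm, QALY SD 0.03. SE(dC) = √((931.25² + 1,331.25²)/178) = 121.8; SE(dQ) = 0.03 × √(2/178) = 0.00318; SE(NB) = √(121.8² + 318²) = 340.5.

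| | dC = −587, dQ = +0.002 | dC = +587, dQ = −0.002 |
|---|---|---|
| Ratio | −293,500 | −293,500 |
| Values excluded by the Fieller set | −74,478 to 174,994 | −74,478 to 174,994 |
| Written rule | reject H0 | reject H0 |
| NB (90% CI) | +787 (227 to 1,347) | −787 (−1,347 to −227) |

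**Step 4: frequency at 3 months.** Simulation with 4,000,000 draws per case; SE(dC) = √((SD₁² + SD₂²)/n) and SE(dQ) = SD × √(2/n). The chance that the net-benefit test rejects is Φ(true NB/SE(NB) − 1.645). Entries are % of trials at QALY SD 0.02 / 0.03 / 0.05.

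(a) Claim withheld although net benefit is significantly positive:

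| True dC, dQ | Cost SDs, n per arm | Withheld |
|---|---|---|
| −783, 0 | plan, 178 | 46 / 26 / 0.5 |
| −783, 0 | plan, 114 | 35 / 11 / 0.01 |
| −587.25, 0 | diluted, 178 | 28 / 7.5 / 0.02 |
| −783, 0 | total-cost 5,000, 178 | 14 / 10 / 4 |
| −783, +0.005 | plan, 178 | 0.9 / 4.5 / 0.3 |

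(b) H0 rejected although true net benefit is zero or negative:

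| True dC, dQ | Cost SDs, n per arm | Written rule | Net-benefit test |
|---|---|---|---|
| 0, −0.01 | plan, 114 | 96 / 78 / 44 | 0.1 or fewer |
| 0, −0.005 | plan, 114 | 53 / 33 / 19 | 0.04 / 0.2 / 0.8 |
| −783, −0.01 | plan, 178 | 24 / 16 / 13 | 0.5 / 1.1 / 2.0 |
| −587.25, −0.01 | diluted, 178 | 52 / 33 / 20 | 0.04 / 0.2 / 0.8 |
| 0, −0.01 | total-cost 5,000, 114 | 40 / 36 / 28 | 0.1 / 0.2 / 0.3 |
| 0, 0 | plan, 178 | about 10 | 5 |
| 0, 0 | total-cost 5,000, 178 | 7.9 / 8.9 / 9.8 | 5 |

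The two rules agreed in every draw with estimated dQ > 0. They disagreed in every draw with estimated dQ < 0 and 100,000 outside the interval.

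**Step 5: correlation.** With cost–QALY correlation from −0.3 to +0.3 (diluted SDs, 178 per arm), withheld claims at dC = −587.25, dQ = 0 are 20–38%, 3.7–13% and 0.1% or less. False claims at dC = 0, dQ = −0.01 are 98–100%, 85–95% and 53–63%.

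**The case against.** The strongest reply is about size.

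- **The worst rates drop the planned saving.** At dC = −783 and dQ = −0.01 the false-claim rate is 24 / 16 / 13%. At dC = −783 and dQ = −0.005, true net benefit is 783 − 500 = +283, so REVAMP really is cost-effective, and rejection against a significantly negative estimate occurs in only 0.2 / 0.6 / 1.5%. This stands, and it is why both sets of rates are shown.
- **A loss of 0.01 QALY in 3 months is large.** It is 0.04 in utility, or 0.50 / 0.33 / 0.20 SD on the assumed SDs, against a primary margin of 1.0/2.8 = 0.36 SD. These are different measures, so the comparison is only a yardstick, but it is fair.
- **The cost basis and SDs are uncertain.** The plan does not say whether total or sleep-related cost enters 2b, gives no QALY SD, and also plans a horizon of up to 2 years that is not examined here. Withheld claims at equal QALYs range from 46% to 0.01%. This stands: the frequency is not established.
- **The rule answers its literal hypothesis.** A ratio of −293,500 is indeed below 100,000. But Aim 2 asks whether REVAMP is cost-effective, and a hypothesis that a dominated strategy satisfies does not answer that.
- **A reader would see the quadrant.** dC and dQ are outcomes in their own right, which limits the harm. Neither enters the decision rule, so correcting the direction after seeing the data would be a departure from the pre-specified test.

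**Conclusion.** The concern holds: the rule is wrong as written. The reversal follows from algebra alone and occurs whenever estimated dQ is negative and the interval excludes 100,000. Its frequency rests on the assumed QALY SDs, the 3-month horizon and the chosen true differences. False claims at dQ = −0.01 run from 13% at the planned saving to 96% at no saving, against about 2% or less for a net-benefit test. Withheld claims at equal QALYs run from near zero to 46%. The consequences are bounded: 2b is secondary, the primary cost hypothesis 2a and its power are untouched, and the rule is sound when estimated dQ is positive. It should be corrected before the analysis, but it does not threaten the trial's main conclusions.

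**What to change.** Restate 2b as H0: 100,000 × dQ − dC ≤ 0 against HA: 100,000 × dQ − dC > 0. Reject if the lower limit of the 90% confidence interval for incremental net monetary benefit exceeds 0, using the mixed-model estimates already planned and their covariance.

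An equivalent alternative keeps Fieller: require the interval to exclude 100,000, and require the ratio to be below 100,000 if estimated dQ > 0 but above 100,000 if estimated dQ < 0.

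Either version changes SAP wording only. Data, models and alpha stay the same.
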